Zogenix is developing a new formulation of fenfluramine hydrochloride, ZX008, for the adjunctive treatment of DS. Studies ZX008-1501 and 1502 are two randomized controlled trials of two fixed doses of ZX008 (Fenfluramine HCl) as an adjunctive therapy in children and young adults with DS. Study 1501 is conducted in North America (Canada and the USA), and 1502 is being conducted in Europe and Australia (Australia, Belgium, Denmark, France, Germany, Italy, Spain, Sweden, and the United Kingdom). The objective of each study is to demonstrate that ZX008 0.8 mg/kg/day is superior to placebo as adjunctive therapy in the treatment of DS in children and young adults based on change in the frequency of convulsive seizures between baseline and the combined Titration and Maintenance Periods (T+M). Study ZX008-1504 is a multicenter, 2-Cohort trial to first assess the pharmacokinetic and safety profile of a single dose of ZX008 (Fenfluramine Hydrochloride) oral solution when added to standard of care (Cohort 1), followed by a randomized, double-blind, placebo-controlled parallel group evaluation of the efficacy, safety, and tolerability of ZX008 as adjunctive antiepileptic therapy to stiripentol treatment in children and young adults with DS (Cohort 2).

The purpose of this Statistical Analysis Plan (SAP) is to outline the planned analyses and presentation of the clinical data from protocol ZX008-1503, dated 08 February 2018 (amendment 4.0), an international, multicenter, open-label, long-term safety study of ZX008 in pediatric and young adult subjects with DS who have successfully completed 14 weeks of treatment in core study ZX008-1501, ZX008-1502, and ZX008-1504 Cohort 2, or successfully completed core study ZX008-1504 Cohort 1, and are candidates for continuous treatment for an extended period of time. In addition, subjects who are >18 to ≤35 years of age at the time of screening, and who meet all other eligibility criteria may be eligible for participation after discussion with the Medical Monitor and sponsor about the potential risks and benefits for receiving ZX008. Participation for these subjects will be at the discretion of the sponsor.

Amendment 3 of this clinical trial extended the initial 12-month study period to 24 months, and Amendment 4 extended the duration to 36 months. Thus, with the implementation of Amendment 4, this clinical trial will consist of an up to 36-month Open-Label Extension (OLE) Treatment Period and a 2-week Post-Dosing

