Period. Subjects who complete this trial will have been treated with ZX008 for a minimum of up to 3 years (including their participation in both the core study and this study). Subjects who did not participate in one of the core studies will undergo a screening period up to 28 days to confirm eligibility prior to receiving their first dose in the OLE Treatment Period. A follow-up electrocardiogram (ECG) and echocardiogram (ECHO) will be performed at 3 and 6 months after study drug discontinuation for early termination and for those subjects who complete the study.

An earlier version of this Statistical Analysis Plan detailed statistical analyses performed as an interim analysis to support the filing of a New Drug Application (NDA) with the US Food and Drug Administration (FDA) and a Marketing Authorisation Application (MAA) with the European Medicines Agency (EMA), based on Amendment 3 of the Study Protocol. The purpose of this updated Statistical Analysis Plan is to provide details of the statistical presentation of the data from this study based on Amendment 4 of the protocol, for the 120-day safety update report following filing of the New Drug Application with the US Food and Drug Administration.

It is planned to perform an analysis of key safety data obtained up to February 15, 2019, for all subjects who entered Study ZX008-1503 by December 31, 2018. The planned interim analysis will present data without revealing the individual treatment groups from the Core studies. The specific list of TFLs that will be presented in the interim analysis will be delineated in the Table of Contents for the TFL shells.

An analysis of Study ZX008-1503 to include only those subjects who entered Study ZX008-1503 from sites in Japan (i.e., Japanese subjects) is planned when all Japanese subjects have reached at least the Month 3 visit. Selected analyses, described in the SAP for the rest of the world, will be performed for this population.

A final analysis and report of all data obtained from this study will be provided within 6 months of completion of the last subject's final study visit.

The planned analyses identified in this SAP will be included in regulatory submissions and/or future manuscripts. Exploratory analyses not identified or defined in the SAP may be performed to support the clinical development program. Any post-hoc or unplanned analyses performed and not identified in this SAP will be documented in the CSR or final report.

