3.2 TREATMENTS

Subjects in the double-blind studies Z008-1501, -1502, and cohort 2 of 1504 who enter Study ZX008-1503 would have transitioned to 0.2 mg/kg during the transition period (between Visits 12 and 13), as described in the 1501 and 1502 Clinical Study Protocols Section 5.5.5, and 1504 Sections 5.5.6 and 5.5.7. Subjects entering from Cohort 1 in Study ZX008-1504 will enter a transition period at a fixed dose of ZX008 0.2 mg/kg/day for up to 24 additional weeks.

In Study ZX008-1503, during the OLE Treatment Period, all subjects will be treated initially with 0.2 mg/kg/day for 1 month to assess effectiveness of this dose in all study subjects. After 1 month at a dose of 0.2 mg/kg/day, the investigator may adjust the dose of each subject based on effectiveness and tolerability. Subjects whose condition worsened relative to their status at the end of the double-blind feeder study could request permission to increase to 0.4 mg/kg/day (max 30mg) after approximately 2 weeks on the 0.2 mg/kg dose. Dose changes should be made in increments of 0.2 mg/kg/day, to a maximum of 0.8 mg/kg/day but not to exceed total dose of 30 mg/day. Dose increases should not occur earlier than every 14 days at each dose level. For subjects in Study ZX008-1504 Cohort 2, the dose titration schedule is 0.2 mg/kg/day, to 0.4, to 0.5 not to exceed 20 mg/day. Dose increases may only occur after a review of the diary and reported AEs, and if, in the investigator's opinion, seizure frequency, severity, and/or duration indicates a change in medication regimen is warranted. Dose decreases for tolerability can occur at the investigator's discretion, in dose amounts and frequency appropriate for the situation. ZX008 dose adjustments outside of these parameters should be discussed with the Medical Monitor prior to initiation.

Effectiveness and safety data will be provided for all subjects treated with ZX008. Data will be summarized by subjects' treatment group in their previous study.

The treatment groups that may be used to summarize the results of the final analysis are presented in Table 1. Groups 1 to 5 are the basic treatment groups.

Table 1. Treatment Groups in Study ZX008-1503 According to Treatment in Feeder Study

Name of Treatment Group	Treatment Group Code	AED Treatment from Feeder study	Feeder Study(s)	Approximate Total Number of subjects at Final Analysis

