Table	14.1.5.1.2	Duration of Treatment Exposure by Sex – Safety Population		Y	
Table	14.1.5.1.3	Duration of Treatment Exposure – Safety Population (Japan)			Y
Table	14.1.5.1.4	Duration of Treatment Exposure by Age Group – Safety Population (Japan)			Y
Table	14.1.5.1.5	Duration of Treatment Exposure by Sex – Safety Population (Japan)			Y
Table	14.1.5.1.6	Duration of Treatment Exposure in ZX008-1502 and ZX008-1503 Combined (Subjects Treated in ZX008-1502 or ZX008-1503) (Japan)			Y
Table	14.1.5.1.7.1	Shift in Assigned ZX008 Dosage in ZX008-1503 by Study Visit – Safety Population			
Table	14.1.5.1.7.2	Shift in Assigned ZX008 Dosage in ZX008-1503 by Study Visit – Safety Population (Japan)			Y
Table	14.1.5.1.8.1	Number of Subjects Receiving ZX008 According to Mean Daily Dose and Duration of Treatment – Safety Population			
Table	14.1.5.1.8.2	Number of Subjects Receiving ZX008 According to Mean Daily Dose and Duration of Treatment – Safety Population (Japan)			Y
Table	14.1.5.1.9.1	Number of Subjects Receiving ZX008 According to Mean Dose (mg/day) and Duration of Treatment – Safety Population			
Table	14.1.5.1.9.2	Number of Subjects Receiving ZX008 According to Mean Dose (mg/day) and Duration of Treatment – Safety Population (Japan)			Y
Table	14.1.5.1.10.1	Number of Subjects Receiving ZX008 According to Actual Dose (mg/kg) and Duration of Treatment – Safety Population			

Table/ Figure/ Listing	Number	Table Header	Included in Interim Analysis?	Include in 120-day safety update report	Included in 1503 Japan safety update report, 2020
Table	14.1.5.1.10.2	Number of Subjects Receiving ZX008 According to Actual Dose (mg/kg) and Duration of Treatment – Safety Population (Japan)			Y
Table	14.1.5.2.1	Compliance to IMP intake – Safety Population	Y	Y	
Table	14.1.5.2.1.1	Compliance to IMP intake – Safety Population (Japan)			Y
Table	14.1.5.2.2	Compliance to IMP intake – mITT Population	Y	Y	
Table	14.1.5.2.2.1	Compliance to IMP intake – mITT Population (Japan)			Y
	14.2	Effectiveness			
	14.2.1	Effectiveness – Convulsive Seizure Frequency			
Table	14.2.1.1.1	Convulsive seizure frequency per 28 days during OLE Treatment Period: Summary Statistics and Tests of Changes from Baseline	Y	Y	
Table	14.2.1.1.2	Convulsive seizure frequency per 28 days during OLE Treatment Period, by Age Group: Summary statistics and Tests of Changes from Baseline – mITT Population	Y		

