You may present two tables using by group of Age Group or present as above, whichever works best for programming.

Programming note: Use the shell for 14.1.5.1 for

Table 14.1.5.1.4
 Duration of Treatment Exposure by Age Group
 Safety Population (Japan)

Table 14.1.5.1.2
Duration of Treatment Exposure by Sex
Safety Population

	Female Subjects	Male Subjects	ALL ZX008 Treated Subjects
Summary Stats			
n	XX	XX	XX
Mean (days)	XX.X	XX.X	XX.X
SD	XX.XX	XX.XX	XX.XX
Median	XX.X	XX.X	XX.X
Min, Max	XX, XX	XX, XX	XX, XX
Duration of Exposure			
<1 month	XX (XX.X%)	XX (XX.X%)	XX (XX.X%)
1 to <3 months	XX (XX.X%)	XX (XX.X%)	XX (XX.X%)
3 to <6 months	XX (XX.X%)	XX (XX.X%)	XX (XX.X%)
6 to <12 months	XX (XX.X%)	XX (XX.X%)	XX (XX.X%)
12 to <18 months	XX (XX.X%)	XX (XX.X%)	XX (XX.X%)
18 to <24 months	XX (XX.X%)	XX (XX.X%)	XX (XX.X%)
24 to <30 months	XX (XX.X%)	XX (XX.X%)	XX (XX.X%)
30 to <36 months	XX (XX.X%)	XX (XX.X%)	XX (XX.X%)
≥36 months	XX (XX.X%)	XX (XX.X%)	XX (XX.X%)

Note: Duration of exposure is calculated from date of first dose in this study to the last date of treatment or data cutoff date for this report, whichever is earlier

Programming note:

Similar to DX22 in ISS, but add rows for 24-30, 30-36;

Programming note: Use the shell for 14.1.5.2 for

Table 14.1.5.1.5
Duration of Treatment Exposure by Sex
Safety Population (Japan)

Table 14.1.5.1.6
Duration of Treatment Exposure in ZX008-1502 and ZX008-1503 Combined
Subjects Treated in ZX008-1502 and ZX008-1503 Combined (Japan)

Time on Treatment (days)	Gp1 (N = XX)	Gp2 (N = XX)	Gp3 (N = XX)	Gp4 (N = XX)	All Subjects (N = XX)
n	XX	XX	XX	XX	XX
Mean	XX.X	XX.X	XX.X	XX.X	XX.X
SD	XX.XX	XX.XX	XX.XX	XX.XX	XX.XX
Min	XX	XX	XX	XX	XX
Q1	XX	XX	XX	XX	XX
Q2 (Median)	XX.X	XX.X	XX.X	XX.X	XX.X
Q3	XX	XX	XX	XX	XX
Max	XX	XX	XX	XX	XX

SD: Standard Deviation. Q1=Lower Quartile; Q2 = Median; Q3=Upper Quartile

Note: Time on treatment (in days) will be calculated per subject as the number of days with IMP intake during the trial. This will be calculated as Date of last IMP intake in ZX008-1502 or ZX008-1503 – Date of first IMP intake in ZX008-1503 + 1. The duration includes the transition period in ZX008-1502.

Table 14.1.5.1.7.1
 Shift in Assigned ZX008 Dosage in ZX008-1503 by Study Visit
 Safety Population

Visit	Last Assigned Dose Prior to Visit	Number of Subjects	Subject dosage (mg/kg) assigned at Visit					
			0.2 mg/kg/day	0.3 mg/kg/day	0.4 mg/kg/day	0.5 mg/kg/day	0.6 mg/kg/day	0.8 mg/kg/day

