Programming Note: Include only events whose start date is between Day -30 (inclusive) and Day -1 (inclusive), counting study days from beginning of OLE Treatment period, not core. There will be no De Novo Column for this table.

Use the Table 14.3.1.9.1 shell for

Table 14.3.1.9.1.1

Non-treatment Emergent Adverse Events Starting between Visits 12 and 13 of the Feeder Study, by MedDRA System Organ Class, Preferred Term and Prior Treatment in Feeder Study Safety Population (Japan)

Table 14.3.1.9.2
TEAEs starting in the 1st month of OLE by System Organ Class, Preferred, Term and Prior Treatment in Feeder Study
Safety Population

MedDRA System Organ Class and Preferred Term	Gp1 (N=xx)	Gp 2 (N=xx)	Gp3 (N=xx)	Gp 4 (N=xx)	Gp5 (N=xx)	De Novo Subjects (N=xx)
Subjects with any TEAE starting in the first month.	XX (XX.X%)	XX (XX.X%)	XX (XX.X%)	XX (XX.X%)	XX (XX.X%)	XX (XX.X%)
System Organ Class 1	XX (XX.X%)	XX (XX.X%)	XX (XX.X%)	XX (XX.X%)	XX (XX.X%)	XX (XX.X%)
Preferred Term 1	XX (XX.X%)	XX (XX.X%)	XX (XX.X%)	XX (XX.X%)	XX (XX.X%)	XX (XX.X%)
Preferred Term 2	XX (XX.X%)	XX (XX.X%)	XX (XX.X%)	XX (XX.X%)	XX (XX.X%)	XX (XX.X%)

TEAE = Treatment-Emergent Adverse Event.

Note: A subject with more than one TEAE with the same preferred term is counted once for that term. A subject with more than one TEAE under a system organ class is counted once for that class.

Programming note:

Include only events starting on or after Day 1 up to Day 30 (counting from beginning of OLE Treatment period, NOT Core).

Use same Table 14.3.1.9.2 shell for

Table 14.3.1.9.2.1
TEAEs starting in the 1st month of OLE by System Organ Class, Preferred, Term and Prior Treatment in Feeder Study
Safety Population (Japan)

Programing note: Use the 14.3.1.9.1 shell to produce the following tables. Include only events starting on or after Study Day31 up to Day 60 (counting from beginning of OLE Treatment period, NOT Core)

Table 14.3.1.9.3
TEAEs starting in the 2nd month of OLE by System Organ Class, Preferred Term and Prior Treatment in Feeder Study
Safety Population

Table 14.3.1.9.3.1
TEAEs starting in the 2nd month of OLE by System Organ Class, Preferred Term and Prior Treatment in Feeder Study
Safety Population (Japan)

Programing note: Use the Table 14.3.1.9.1 shell for the following tables. Include only events starting on or after Study Day61 up to day 90(counting from beginning of OLE Treatment period, NOT Core)

Table 14.3.1.9.4

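### The combined ZX008-1502 and ZX008-1503 exposure table for Japan starts its clock at the first ZX008-1503 dose, so for rolled-over subjects it reports ZX008-1503 exposure only

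*SAP*

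**What the plan says.** The list of planned outputs in SAP Appendix 1 includes Table 14.1.5.1.6, flagged for the 2020 Japan report, under the title "Duration of Treatment Exposure in ZX008-1502 and ZX008-1503 Combined (Subjects Treated in ZX008-1502 or ZX008-1503) (Japan"). The shell itself describes the population differently: "Subjects Treated in ZX008-1502 and ZX008-1503 Combined (Japan").

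The note under the shell computes time on treatment as "Date of last IMP intake in ZX008-1502 or ZX008-1503 – Date of first IMP intake in ZX008-1503 + 1". The sentence after it reads "The duration includes the transition period in ZX008-1502".

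SAP Section 3.2 fixes when that transition happens. Subjects from the double-blind studies who enter ZX008-1503 "would have transitioned to 0.2 mg/kg during the transition period (between Visits 12 and 13") of the core study. SAP Section 6.1.4.3 starts the ZX008-1503 day count at the first open-label dose, so the transition lies wholly before the start date in the formula.

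SAP Section 6.2.4.1 restricts exposure summaries to time in ZX008-1503. It does not mention the combined table. The shell note is the only specification of it, and nothing elsewhere in the SAP gives another start date.

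**The concern.** The title, the formula and the sentence on the transition cannot all hold. A clock that starts at the first ZX008-1503 dose cannot contain days that came before it. A programmer who follows the formula will produce, for each rolled-over subject, the number already reported in Table 14.1.5.1.3 (Japan exposure in ZX008-1503), under a heading that says the two studies were combined.

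This is the only listed Japan table meant to describe exposure across both studies. The Japan outputs also include adverse event tables that reach back into the double-blind period (14.3.1.10.1.1 and 14.3.1.10.2.1). Readers of those tables would naturally look to this one for the matching exposure, and as printed it omits the double-blind days.

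**Working it through.** The SAP prints no exposure figure to reproduce, so the check applies the printed formula to a typical subject and compares it with the same formula started at the first IMP intake in either study.

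**Inputs**
- Core treatment: 14 weeks = 98 days. SAP Section 1 describes entrants as those "who have successfully completed 14 weeks of treatment in core study ZX008-1501, ZX008-1502, and ZX008-1504 Cohort 2".
- Transition length: not given in days. Assumed 0, 14 or 30 days. The upper end follows the programming note for Table 14.3.1.9.1, which selects adverse events between Visits 12 and 13 with "Include only events whose start date is between Day -30 (inclusive) and Day -1 (inclusive").
- Open-label days: 90 for Month 3, because the Japan analysis is "planned when all Japanese subjects have reached at least the Month 3 visit"; 360 for about 12 months; 1085 for Month 36 (the study day in SAP Table 4).
- No gap between the last ZX008-1502 dose and the first ZX008-1503 dose (assumption).

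**Formulas**
- As printed: last ZX008-1503 intake − first ZX008-1503 intake + 1 = open-label days.
- Combined: last intake − first intake in either study + 1 = 98 + transition + open-label days.
- Share lost = (98 + transition) ÷ combined.

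**Subject on active drug in ZX008-1502**

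| Open-label days (= printed result) | Transition (assumed) | Combined | Days lost | Share lost |
|---|---|---|---|---|
| 90 | 0 | 188 | 98 | 52.1% |
| 90 | 14 | 202 | 112 | 55.4% |
| 90 | 30 | 218 | 128 | 58.7% |
| 360 | 0 | 458 | 98 | 21.4% |
| 360 | 14 | 472 | 112 | 23.7% |
| 360 | 30 | 488 | 128 | 26.2% |
| 1085 | 0 | 1183 | 98 | 8.3% |
| 1085 | 14 | 1197 | 112 | 9.4% |
| 1085 | 30 | 1213 | 128 | 10.6% |

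**Subject on placebo in ZX008-1502.** The 98 core days were not ZX008 exposure, so only the transition is lost. At Month 3: 0 ÷ 90 = 0%, 14 ÷ 104 = 13%, 30 ÷ 120 = 25%.

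**De novo subject.** There is no ZX008-1502 exposure to lose, so the printed formula is correct.

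**Subject treated in ZX008-1502 only**, if the population is the one in the list of outputs. There is no first ZX008-1503 intake, so the formula gives no value. A subject with exactly the 14 core weeks and no transition should show 98 days.

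**Use of the last ZX008-1502 date.** The formula allows this. For a rolled-over subject with no gap, the last ZX008-1502 intake is the day before the first ZX008-1503 intake, so the result is −1 + 1 = 0 days. With a gap it is negative.

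**The case against.** The strongest reply is that this is a visible slip in one descriptive shell. The title and the next sentence show what was intended, the ZX008-1503 exposure tables for Japan (14.1.5.1.3 to 14.1.5.1.5) are unaffected, and no test or decision rule uses the result. That lowers the severity but does not remove the error, because the intention can be read in more than one way. With a 14-day transition at Month 3, starting at the transition gives 14 + 90 = 104 days and starting at the first ZX008-1502 dose gives 202. For former placebo subjects, the choice also decides whether 98 placebo days count.

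The size also has limits. Month 3 is a minimum, so subjects enrolled earlier lose a smaller share. De novo subjects from Japan are expected (Tables 14.4.1.4.1 and 14.4.6.3.1 are flagged for the same report). The mix of de novo, former placebo and former active subjects is not stated, so the shortfall in the table's overall mean cannot be computed.

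Three stronger readings are tempting and are not supported:
- *Event rates would be inflated.* No rate in the SAP is specified on this table. Table 14.2.8.1 uses subject-years of follow-up for the subjects in its own columns, and adverse event percentages use Safety Population counts.
- *The table fails for subjects treated only in ZX008-1502.* That holds under the wording in the list of outputs, which joins the studies by *or*. The shell header joins them by *and*, which would exclude such subjects, and nothing in the SAP says that any Japanese subject was treated in ZX008-1502 alone.
- *The table should count ZX008 days by arm.* The note counts IMP intake. SAP Sections 6.3.1.3 to 6.3.1.5 say parts of the core studies remain blinded for the Japanese interim, so arm-specific dates may not be available.

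**Conclusion.** The formula is wrong as written. Its start date contradicts the table's title and the sentence that follows it, and no other part of the SAP corrects it. For rolled-over subjects it yields ZX008-1503 exposure only. The omission is 98 to 128 days of IMP intake per subject who completed the 14 core weeks. As a share of combined ZX008 exposure, it is about 52% to 59% at Month 3 and about 21% to 26% at 360 days for subjects from an active arm, and 0% to 25% at Month 3 for former placebo subjects. These figures rest on an assumed transition of 0 to 30 days and no gap between the studies.

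The consequence is a misreported descriptive table in the Japan report, not a change to any inference. It should be fixed before the table is produced or relied on.

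**What to change.** 1. In the note to Table 14.1.5.1.6, change the start date to the first IMP intake in ZX008-1502 or ZX008-1503, whichever is earlier, and the end date to the last IMP intake in either study, whichever is later.
2. State whether placebo days count. If arms are still blinded at the Japan interim, label the result as time on any IMP.
3. Use one population label in the list of outputs and in the shell header. If subjects treated in either study are meant, say that ZX008-1502-only subjects use their ZX008-1502 dates.
4. In the same edit, check the Group 4 column: SAP Table 1 draws Group 4 from ZX008-1504 Cohort 2, not from ZX008-1502.

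The cost is a short correction to one shell and its programming, plus a sponsor decision on placebo days and on the population. No new data collection is needed, although the program must read ZX008-1502 dosing dates.

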6. STATISTICAL METHODOLOGY

6.1 STATISTICAL AND ANALYTICAL ISSUES

6.1.1 Statistical Methods

All data on safety, effectiveness and exploratory endpoints will be summarized. Continuous data will be summarized using descriptive statistics including number of subjects, means, standard deviations, medians, lower and upper quartiles, and ranges. Categorical variables will be summarized with frequencies and percentages.

Effectiveness and safety data may be summarized by treatment group in previous study as described in Section 3.2 in this SAP. The effectiveness and safety data will also be summarized by age group as described in Section 6.1.3, and overall.

Point and interval estimates (95% confidence intervals) will be calculated for within treatment changes from baseline for key parameters as warranted. These within-treatment changes from baseline comparisons should be interpreted with caution, as any effect of treatment may be confounded with the time-course of disease or other factors. The primary evidence for efficacy and safety of ZX008 is based on the treatment comparisons from the double-blind studies, while the data from this OLE study provides evidence of long-term safety and effectiveness.

Confidence intervals and/or p-values, where provided for between treatment group differences, should be regarded as descriptive and not for formal inferential purposes.

All descriptive statistical analyses will be performed using SAS statistical software (Version 9.3, unless otherwise noted). Adverse events will be coded using the most recent MedDRA version available at the time of analysis. Concomitant medications will be coded using the most recent version of World Health Organization (WHO) Drug.

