6.3.1.2 Changes from Baseline

In all seizure analyses, the Baseline (Core) value will be the baseline used. These analyses exclude the subjects from Study ZX008-1504 Cohort 1. For any of the variables defined in the previous section, the change from baseline for any individual subject will be calculated as

$$\text{CCSF} = \text{Post-baseline value} - \text{CSF}_{\text{BC}}$$

The percentage change from baseline for any individual subject will be calculated as

$$\text{PCCSF} = (\text{Post-baseline value} - \text{CSF}_{\text{BC}}) * 100 / \text{CSF}_{\text{BC}}$$

The key effectiveness measures are CSF_{E1} and CSF_{E2} . Summary statistics for the changes from baseline and the percentage changes from baseline will also be presented. A Wilcoxon signed rank test will be used to assess the significance of the change from baseline. Given that baseline refers to the period prior to initiation of double-blind treatment in the Core study, it is expected that long-term treatment with ZX008 will lead to a reduction in convulsive seizure frequency. If we designate the mean baseline (core) CSF by μ_{BC} , and the mean for CSF_{E1} and CSF_{E2} by μ_{E1} and μ_{E2} , respectively, the key effectiveness objective is to test the null hypothesis

$$H_0: \mu_{\text{E1}} - \mu_{\text{BC}} = 0,$$

Against the alternative

$$H_A: \mu_{\text{E1}} - \mu_{\text{BC}} \neq 0,$$

Rejection of the null hypothesis in favor of the alternative, in the presence of a statistically significantly smaller mean convulsive seizure frequency during OLE Treatment (two-sided p-value < 0.05) will be regarded as evidence of a treatment benefit.

In a similar manner, each of the changes over time will be summarized and assessed for statistical significance.

The summary statistics and statistical testing will also be presented by age group.

A graph of the CSF for baseline (Core), Core Study (T+M), and during OLE Month 1 ...36 will be generated, and another graph of the percentage changes from baseline may be plotted.

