N	XX	XX	XX	XX	XX	XX
Mean (SD)	XX.X (XX.XX)	XX.X (XX.XX)	XX.X (XX.XX)	XX.X (XX.XX)	XX.X (XX.XX)	XX.X (XX.XX)
Median	XX.X	XX.X	XX.X	XX.X	XX.X	XX.X
Min, Max	XX.X, XX.X	XX.X, XX.X	XX.X, XX.X	XX.X, XX.X	XX.X, XX.X	XX.X, XX.X
ENDPOINT2: Month02-EOS Change from Baseline						
N	XX	XX	XX	XX	XX	XX
Mean (SD)	XX.X (XX.XX)	XX.X (XX.XX)	XX.X (XX.XX)	XX.X (XX.XX)	XX.X (XX.XX)	XX.X (XX.XX)
Median	XX.X	XX.X	XX.X	XX.X	XX.X	XX.X
Min, Max	XX.X, XX.X	XX.X, XX.X	XX.X, XX.X	XX.X, XX.X	XX.X, XX.X	XX.X, XX.X
ENDPOINT2: Month02-EOS % Change from Baseline						
N	XX	XX	XX	XX	XX	XX
Mean (SD)	XX.X (XX.XX)	XX.X (XX.XX)	XX.X (XX.XX)	XX.X (XX.XX)	XX.X (XX.XX)	XX.X (XX.XX)
Median	XX.X	XX.X	XX.X	XX.X	XX.X	XX.X
Min, Max	XX.X, XX.X	XX.X, XX.X	XX.X, XX.X	XX.X, XX.X	XX.X, XX.X	XX.X, XX.X
P-value[4]	X.XXX	X.XXX	X.XXX	X.XXX	X.XXX	X.XXX

*Includes subjects randomized to placebo and all doses of ZX008 during DB.

** For De Novo subjects, the baseline period is the 28 days prior to dosing in ZX008-1503. Change from baseline for this group is calculated relative to this baseline period.

T+M = Titration + Maintenance; OLE = Open-label extension; SD = Standard deviation; Chg = Change; EOS = End of study

Data from core study includes subjects on Placebo as well as ZX008.

[1] Baseline=Baseline prior to double-blind treatment in the core study or 28 days prior to dosing in ZX008-1503 for De Novo Subjects. Subjects in 1504-C1 do not have a Baseline(Core).

[2] Core Study (T+M) is the entire Titration+Maintenance Period during the Core study; does not include the transition period.

[3] Core Study Final Week of T+M is the last 7 days of the T+M period.

[4] P-value for within group % change from baseline is based on Wilcoxon signed rank test that the % change from baseline is statistically significantly different from 0.

Programming note:

P-values are only calculated for the OLE Period, starting from Month1 onward. The p-value will be obtained for the percentage change from baseline, not the change from baseline. Please see SAP section 6.1.6. It does matter whether we attach the p-value to the change stats or the percent change stats; Zogenix wants the p-value from the analysis of the percentage changes from baseline. Use the round function to get the percentage change to 3 or 4 decimal places before calculating pccs25yn, pccs50yn, pccs75yn and especially pccs00yn.]

Code to get p-value for percentage change at each time point:: calculate the percentage change from baseline:

For example:

```

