Mean (SD)	XX.X (XX.XX)	XX.X (XX.XX)	XX.X (XX.XX)	XX.X (XX.XX)
Median	XX.X	XX.X	XX.X	XX.X
Min, Max	XX.X, XX.X	XX.X, XX.X	XX.X, XX.X	XX.X, XX.X

	ZX008 Low Mean Daily Dose* (>0 - <0.4 mg/kg) (N = XX)	ZX008 Medium Mean Daily Dose* (0.4 – 0.6 mg/kg) (N = XX)	ZX008 High Mean Daily Dose* (>0.6 mg/kg) (N = XX)	Any ZX008 OL Dose* (N = XX)
ENDPOINT1: Overall OLE Treatment Period % Change from Baseline				
N	XX	XX	XX	XX
Mean (SD)	XX.X (XX.XX)	XX.X (XX.XX)	XX.X (XX.XX)	XX.X (XX.XX)
Median	XX.X	XX.X	XX.X	XX.X
Min, Max	XX.X, XX.X	XX.X, XX.X	XX.X, XX.X	XX.X, XX.X
P-value[4]	X.XXX	X.XXX	X.XXX	X.XXX
ENDPOINT2: Month02-EOS				
N	XX	XX	XX	XX
Mean (SD)	XX.X (XX.XX)	XX.X (XX.XX)	XX.X (XX.XX)	XX.X (XX.XX)
Median	XX.X	XX.X	XX.X	XX.X
Min, Max	XX.X, XX.X	XX.X, XX.X	XX.X, XX.X	XX.X, XX.X
ENDPOINT2: Month02-EOS Change from Baseline				
N	XX	XX	XX	XX
Mean (SD)	XX.X (XX.XX)	XX.X (XX.XX)	XX.X (XX.XX)	XX.X (XX.XX)
Median	XX.X	XX.X	XX.X	XX.X
Min, Max	XX.X, XX.X	XX.X, XX.X	XX.X, XX.X	XX.X, XX.X
ENDPOINT2: Month02-EOS % Change from Baseline				
N	XX	XX	XX	XX
Mean (SD)	XX.X (XX.XX)	XX.X (XX.XX)	XX.X (XX.XX)	XX.X (XX.XX)
Median	XX.X	XX.X	XX.X	XX.X
Min, Max	XX.X, XX.X	XX.X, XX.X	XX.X, XX.X	XX.X, XX.X
P-value[4]	X.XXX	X.XXX	X.XXX	X.XXX

T+M = Titration + Maintenance; OLE = Open-label extension; SD = Standard deviation; Chg = Change; EOS = End of study

Data from core study includes subjects on Placebo as well as ZX008

*Note: The calculated (weight adjusted) daily doses over the entire OLE period were averaged to get a mean dialy dose, which was then categorized as follows: >0 – <0.4 mg/kg = Low; 0.4 – 0.6 mg/kg = Medium; >0.6 mg/kg = High

[1] Baseline=For subjects who participated in a double-blind study, the Baseline prior to double-blind treatment in the core study. Subjects in 1504-C1 do not have a Baseline(Core), and are not included in this table. For De Novo subjects, the baseline period is the 28 days prior to dosing in ZX008-1503. Change from baseline for this group is calculated relative to this baseline period.

[2] Core Study is the entire Titration+Maintenance Period during the Core study; does not include the transition period.

[3] Core Study Final Week of T+M is the last 7 days of the T+M period.

[4]P-value for within group change from baseline is based on Wilcoxon signed rank test that the change from baseline is statistically significantly different from 0.

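### The key convulsive-seizure test is on the change from baseline in Section 6.3.1.2 but is programmed on the percentage change, which gives a wrong two-sided p-value and loses power

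*SAP*

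**What the plan says.** Section 6.3.1.2 defines the change (CCSF) and the percentage change (PCCSF) as separate variables and then states: "A Wilcoxon signed rank test will be used to assess the significance of the change from baseline". It adds that "the key effectiveness objective is to test the null hypothesis" of equal mean CSF in the OLE and at baseline. Its decision rule is "Rejection of the null hypothesis in favor of the alternative, in the presence of a statistically significantly smaller mean convulsive seizure frequency" during OLE treatment, closing with "two-sided p-value < 0.05) will be regarded as evidence of a treatment benefit".

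The shells in Appendix 1 differ:

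- **Table 14.2.1.1.1.** Footnote 4, the programming note and the sample code all take the p-value from the percentage change: "The p-value will be obtained for the percentage change from baseline, not the change from baseline". The note itself says "It does matter whether we attach the p-value to the change stats or the percent change stats". This shell also produces Tables 14.2.1.1.2, 14.2.1.1.6 and 14.2.1.1.7.
- **Table 14.2.1.1.3 (by mean daily dose).** Footnote 4 reads "P-value for within group change from baseline is based on Wilcoxon signed rank test". The p-value is printed on both rows at Month 1, but only on the percentage-change row at Month 2 and for both endpoints.
- **Table 14.2.6.1 (non-convulsive seizures).** The test is on the change.

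Section 6.10 does not reconcile these. Section 6.1.1 says within-group comparisons "should be interpreted with caution, as any effect of treatment may be confounded with the time-course of disease or other factors".

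**The concern.** A programmer following the shell and a reader following Section 6.3.1.2 would obtain different p-values for the same key endpoint. The choice of scale is not neutral. The signed-rank test has its nominal level only if the tested variable is symmetric about zero when nothing has changed, and percentage change is not: halving is -50%, doubling is +100%. The null in Section 6.3.1.2 also concerns means, which a signed-rank test on either scale does not test. At stake are the p-values at every OLE interval and for both endpoints, in the overall, age-group and Japan tables.

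**Working it through.** **Inputs.** From the SAP: two-sided 0.05 (Section 6.3.1.2), and Groups 1-4 of Table 1, 120 + 80 + 80 + 40 = 320, with 80 in each of Groups 2 and 3. Assumed, because the SAP gives no CSF mean or SD: lognormal rates, median 15 or 20 per 28 days, between-subject log-SD 1.0, and log-ratio SD from 0.5 to 1.0. A within-subject log-SD of s in each period gives a log-ratio SD of s√2.

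**Step 1: why the level fails.** Let R = CSF in the OLE / CSF at baseline, so PCCSF = 100(R - 1). With no change, log R is symmetric about 0. The signed-rank statistic is driven by p, the probability that two subjects' percentage changes sum to more than zero, that is R1 + R2 > 2. Since (R1 + R2)/2 ≥ √(R1R2), and R1R2 > 1 with probability 1/2, p always exceeds 1/2. For normal log R, numerical integration gives p = 0.563, 0.591 and 0.606 at SD 0.5, 0.8 and 1.0.

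**Step 2: size by hand.** Shift of the statistic ≈ [n(n-1)/2](p - 0.5). Null SD = √[n(n+1)(2n+1)/24].

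- n=320: 51,040 pairs, null SD = √2,743,480 = 1,656. At SD 0.5: 51,040 × 0.0634 / 1,656 = 1.95, so P(reject) ≈ P(N > 1.96 - 1.95) ≈ 0.50.
- n=80: 3,160 pairs, null SD = √43,470 = 208.5. At SD 0.5: 3,160 × 0.0634 / 208.5 = 0.96, so P(reject) ≈ P(N > 1.00) ≈ 0.16.

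**Step 3: simulation, no change, two-sided rejection rate.**

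| Log-ratio SD | % change, n=80 | % change, n=320 |
|---|---|---|
| 0.5 | 0.15-0.16 | 0.49-0.50 |
| 0.8 | 0.28-0.29 | 0.81 |
| 1.0 | 0.37-0.38 | 0.91 |

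The hand calculation agrees. Separate runs under similar assumptions gave 46-89% at n=320 and 18-35% at n=80. The test on the change gave 0.042-0.055 and the test on the difference in log(CSF+1) gave 0.045-0.059.

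**Step 4: direction.** Read from the ranks, false rejections towards a reduction were 0.000-0.008. Requiring a significantly smaller mean as well (operationalised as a paired t-test, since the SAP names no test of the mean), false benefit was at most 1.1%, at n=320 and SD 1.0.

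**Step 5: power.** True 20% reduction, n=120, s = 0.5 (log-ratio SD 0.71): 0.38 on percentage change, 0.85 on change, 0.91 on log(CSF+1). The two versions the SAP specifies gave different significance verdicts in 47% of runs. The gap depends on variability: for a 30% reduction at n=120 it is 0.99 against 1.00 at s = 0.3, and 0.35 against 0.93 at s = 0.7.

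**The case against.** The strongest reply is that this is a secondary, uncontrolled endpoint in a safety study, that Section 6.1.1 already urges caution, and that every magnitude above rests on assumed variability. That stands and limits the severity. It does not remove the contradiction, and the asymmetry in Step 1 holds at any variability.

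A reader might infer more than the documents support:

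- **That false claims of benefit are inflated.** The excess rejections point to an increase, and the rule also requires a significantly smaller mean. Only by dropping the words on significance and accepting a numerically smaller mean does false benefit rise, to 0.11-0.42 at n=320. That is a reason to state how direction is judged, not a property of the rule as written.
- **That Tables 14.2.1.1.1 and 14.2.1.1.3 would print conflicting p-values for the key endpoints.** Both place them on the percentage-change row. Only footnote 4 and the Month 1 row of the second table depart from this, and the columns are different groupings.
- **That the sign reversal in the sample code matters.** It cannot alter a two-sided signed-rank p-value. Reading `anal` after building `temp` is a naming slip in example code.
- **That Section 6.1.1 rules out any evidence of benefit.** It asks for caution and places the primary efficacy evidence in the double-blind studies. The conflict with Section 6.3.1.2 is one of strength of wording.
- **That a log-ratio test should replace the stated one.** Its 5% level also assumes exchangeable periods. In overdispersed count models with equal true rates and a 42-day baseline against a long OLE period, it rejected 22-34% at n=80 and 82-88% at n=320. In one of those models the absolute change rejected 7.5% and 30%.

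**Conclusion.** The plan is wrong as written. The SAP body and the shell specify different tests of the key effectiveness endpoint, and the programmed one does not hold its two-sided 5% level when nothing has changed. The direction of the error follows from the bound at -100%; its size depends on the assumed log-ratio SD. The practical damage is a p-value that cannot be read at face value and reduced power for moderate reductions, with little loss where the effect is large relative to variability. This should be fixed before the final analysis; it does not touch the primary safety objective.

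**What to change.** 1. Take the p-value from the signed-rank test on the change (CCSF), as Section 6.3.1.2 already states. Apply this to the footnotes, p-value rows, programming note and code of Tables 14.2.1.1.1 and 14.2.1.1.3, and to every table that reuses those shells. Keep percentage change as summary statistics only.
2. Correct the note's reference to Section 6.1.6, which covers visit windows, and the dataset name in the code.
3. Restate the null as the change being symmetric about zero, with direction read from the sign of the signed-rank statistic or the Hodges-Lehmann estimate.
4. Reword the benefit sentence in Section 6.3.1.2 as descriptive, in line with Section 6.1.1.
5. Optionally add the difference in log(CSF+1) as a sensitivity analysis.

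Neither scale cures unequal period lengths or regression to the mean, and the text should say so. The cost is SAP wording and a few lines of code. The downside is that p-values will differ from those already run at earlier interims, so an explanatory note is needed.
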